### **6.2 Safety Assessments**

The description, severity, and device relatedness of any AE or SAE during the study will be recorded. In the event of any device issues, the event will be recorded. Safety reporting will be conducted as described in this protocol.

## **7. QUALIFICATION AND TRAINING PLAN**

### **7.1 Staff Qualifications**

All members of the study staff participating in the conduct of the investigation shall be qualified by education, training and/or experience to perform their tasks, and this shall be documented appropriately, per ISO 14155. If study staff or PI qualification lapses, the Sponsor will work with the site to requalify the respective role or ensure the duties are reassigned appropriately by the site. The Sponsor reserves the right to disqualify a PI with appropriate justification, such as repeated issues that impact participant safety and data integrity.

## **7.2 Training Plan for the Protocol and Research Device/Product**

Before starting the study, the study staff will be trained on the clinical investigation requirements set forth in this study protocol.

The following training information will be collected in the training log prior to study enrollment:

- Title of Training
- Target audience (who will be trained)
- Training content (including device operation, protocol review and understanding)

Study staff directly operating or maintaining the research device or product will be trained based on the current available operator manual and Device Training provided by the Sponsor.

The Principal Investigator will be ultimately responsible for execution of this study per the protocol and for device use in this study by members of the study staff.

## **8. SAFETY**

### **8.1 Anticipated Adverse Events**

#### **8.1.1 Non-invasive, or transcutaneous, ultrasound exams**

Non-invasive diagnostic ultrasound involves minimal risk because it does not utilize X-rays or other types of ionizing radiation. Even though manifestation of risks during diagnostic ultrasound is rare, diagnostic ultrasound can produce effects on the body, such as:

Risk	Description	Likelihood
Tissue warming	In transcutaneous ultrasound, the probe may heat up slightly, causing sensation of warmth or heat of the skin at the site of the contact with probe.	Rare.
Cavitation	Formation of small pockets of gas in body fluids or tissues.	Rare.
Skin/tissue irritation or injury	Reddening, scraping, stretching, pulling, or other sensations of the skin/tissue that may cause minor discomfort. Contact with gel or disinfectants may cause allergic reactions or skin irritations.	Uncommon.
Bruising or Abrasion (tears) in skin or tissue	Skin bruising or abrasion/tearing caused by probe placement and movement across the tissue.	Uncommon.
Infection	There is a very low risk of infection from cross contamination of probe surface or gel, which is mostly theoretical in case of intact skin.	Rare.

The risk of these adverse effects is not expected to be greater for subjects in this study than those encountered during routine diagnostic ultrasound procedures conducted outside of the study.

The formation of an ultrasound image necessarily requires the exposure of regions of interest to ultrasonic energy, part of which is absorbed in the tissue through which it propagates, and part is reflected back to the transducer (probe) and forms the image. Biological effects of diagnostic ultrasound include heating of the tissues by absorbed ultrasound energy and the risk of cavitation from pressure gradient passing through the tissue (such as lung tissue and bowels with gas that may enter the ultrasound field of view during cardiac exams). The cavitation effects of acoustic energy are most pronounced at lower than diagnostic ultrasound

# Study Title: GE Cardiovascular Ultrasound Device Evaluation

Study Number: 217021760

frequencies (in kHz range, not MHz range) and the human tissues have less nucleation sites and higher viscosity than water and the negative pressures from diagnostic ultrasound are lower than most testing done to evaluate cavitation.

## 8.1.2 TEE Ultrasound Imaging

TEE probes are optimized to ensure acceptable safety in terms of externalatraumatic smoothness, probe size, trackability, steerability and maneuverability-stiffness while allowing adequate diagnostic imaging performance. The probes are also designed for robustness to foreseeable mishaps and reprocessing throughout their service life. User attentiveness is still essential for safe operation of the TEE probes.

Invasive ultrasound scans carry inherent risks associated with invasive nature of the procedure, such as:

Risk	Description	Likelihood
Perforation	
Injury to the esophagus, throat and mouth could occur if the users are not appropriately trained in endoscopic procedures and familiar with the probe at hand. There are varied mechanisms for an esophageal perforation during a TEE exam. Direct mechanical trauma can cause an esophageal perforation; from a blind insertion and advancement of the probe; size discrepancy of the probe tip relative to the esophagus, and from a wide range of probe tip flexion and manipulation required to obtain certain images. Mechanical injury to esophageal tract is therefore an inherent risk due to the nature of the TEE procedure. The incidence, nature and severity of esophageal tears/perforations associated with endoscopic procedures are well characterized.Injuries vary from self-resolving (local minor bleeding), to life-threatening (perforation, major bleeding, infection or death) requiring surgery or medical treatment. Significant injuries are uncommon when patient is low-risk, underlying the importance of careful assessment of suitability of the TEE procedure for a particular patient.
 
Indirect trauma of the GI tract may be related to excessive or prolonged, continuous pressure at the TEE probe-mucosal interface, resulting in tissue ischemia and necrosis. The risk can be minimized by relaxing the pressure and moving the probe tip to a less sensitive area. This may occur particularly during cardiac surgical procedures, when the TEE probe is stationed in the thoracic esophagus, for long durations.
	Rare.
Bleeding	
Overstimulation of mucosa by manipulations of the TEE probe necessary to perform the examination may lead to tears ranging from minor to serious.
 
The external surface of the probe could be damaged through impact, which could expose sharp edges and lead to bleeding. Pre-procedure inspection of the probe for defects is essential to minimize this risk, as these conditions are easily noticeable by user.
	Rare.
Infection	
Cross contamination could occur if the probe is not properly reprocessed or is damaged or worn in such a way that micro-organisms or disinfection chemicals could collect inside the probe to be released when intubated. Requirements for high-level disinfection must be met for patient contact areas.
 
Note, there is no adequate means to disinfect a probe that has been contaminated by prions, such as Creutzfeldt Jacob's disease. In such case,
	Rare.

# Study Title: GE Cardiovascular Ultrasound Device

## Evaluation

Study Number: 217021760

	the contaminated device/probe MUST BE discarded in accordance with local biologic waste hazard procedures.	
Bruising	Irritation and discomfort of the throat due to placement and movement of the probe.	Uncommon.
Tissue warming	In case of invasive ultrasound, the probe may heat internal tissue (e.g. esophageal wall), but this would not be detectable to the subject. The system continuously monitors probe temperature and shuts the probe down automatically if unsafe temperature is detected well before a burn is expected.	Rare.
Chemical burns	Chemical burns can occur if the probe is not completely rinsed from residue of harsh disinfectants.	Rare.
Electric shock	There are electric currents present inside the TEE probe. In extremely rare cases of loss of integrity of the probe the patient may get exposed to the risk of electric shock. Structural integrity check using leakage current are incorporated as part of reprocessing, thus this risk is minimized.	Rare.
Damage to dental fixtures	Damage to teeth and dental prosthetics is also a concern when removing the probe or using bite guards.	Uncommon.

The investigational device is being used in addition to the standard of care device, so there is an increased risk of AEs associated with this extended procedure. The additional scan does not have risks beyond the standard of care procedure, but the secondary intubation may increase the overall likelihood of events occurring.

The Vivid E95 [REDACTED] ultrasound system is investigational and has not been cleared by the FDA. However, it has been developed based on technologies that are well understood and used in commercial ultrasound systems developed and marketed by GEHC.

There is always a chance of unexpected risks. Throughout the study, the Sponsor will evaluate and update safety information in study documents.

## 8.2 Adverse Event Definitions

**Adverse Event (AE):** any untoward medical occurrence, unintended disease or injury, or untoward clinical signs (including abnormal laboratory findings) in subjects, users or other persons, whether or not related to the investigational medical device and whether anticipated or unanticipated. This includes events related to the investigational device or the comparator and to the procedures involved. For users or other persons, this is restricted to events related to the use of investigational medical devices or comparators.

**Serious Adverse Event (SAE):** an AEs that led to death; led to a serious deterioration in the health of the subject, users, or other persons as defined by one or more of the following: a life-threatening illness or injury, a permanent impairment of a body structure or a body function including chronic disease, or in-patient or prolonged hospitalization, or medical or surgical intervention to prevent life-threatening illness or injury or permanent impairment to body structure or a body function; or led to fetal distress, fetal death or a congenital abnormality or birth defect including physical or mental impairment. Planned hospitalization for a pre-existing condition, or a procedure required by the protocol without serious deterioration in health, is not considered a SAE.

# Study Title: GE Cardiovascular Ultrasound Device Evaluation

Study Number: 217021760

**Adverse Device Effect (ADE):** an AEs related to the use of an investigational or comparator medical device. This includes any AEs resulting from insufficient or inadequate instructions for use, deployment, implantation, installation, or operation, or any malfunction of the investigational medical device. This includes any event that is a result of a user error or intentional misuse of the investigational device.

**Serious Adverse Device Effect (SADE):** an adverse device effect that has resulted in any of the consequences characteristic of a SAE.

**Unanticipated serious adverse device effect (USADE):** a serious adverse device effect, which by its nature, incidence, severity, or outcome has not been identified in the current risk assessment. (Note, the ISO14155 term *USADE* encompasses the FDA term *Unanticipated Adverse Device Effect* or *UADE*, and shall be reported in accordance with FDA requirements.)

**Serious health threat:** signal from any AE or device deficiency that indicates an imminent risk of death or a serious deterioration in the health of subjects, users or other persons, and that requires prompt remedial action for other subjects, users or other persons.

## 8.3 Documentation of Adverse Events

All AEs, including all SAEs, are required to be collected, investigated, and documented. AEs will be collected from the time the ultrasound exam begins with the investigational device to the time the subject leaves the scan room. All AEs will be followed through to their resolution. Documentation will include:

- Description of Event
- Date of onset
- Outcome, including date of resolution, unless resolution does not occur during study reporting period. In the instance that resolution does not occur, the status of the AE will be documented
- Severity (mild, moderate, or severe)
  - *Mild:* Symptom(s) barely noticeable to the subject or does not make the subject uncomfortable. The AE does not influence performance or functioning. Prescription drugs are not ordinarily needed for relief of symptom(s).
  - *Moderate:* Symptom(s) of a sufficient severity to make the subject uncomfortable. Performance of daily activities is influenced. Treatment of symptom(s) may be needed.
  - *Severe:* Symptom(s) of a sufficient severity to cause the subject severe discomfort. Treatment for symptom(s) may be given.
- Serious (yes/no)
- Causal relationship to investigational or comparator medical device? (not related, possibly related, or related)
  - *Not related:* The AEs is reasonably expected to be related to (or caused by) a concurrent illness, effect of another device/drug or other cause, and is unlikely related to the investigational product.
  - *Possibly related:* The AEs is reasonably expected to be related to the investigational product, and an alternative etiology is equally or less likely compared to the potential relationship to investigational product.
  - *Related:* There is a strong relationship to investigational product or recurs on re-challenge, and another etiology is unlikely or there is no other reasonable medical explanation for the event.
- Causal relationship to investigational procedure? (not related, possibly related, or related)
- Treatment given and/or action taken
- Anticipated (yes/no)
- Signals from AE that might indicate a serious health threat.

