## **2.3 Concomitant / Ancillary Administrations**

### **2.3.1 Medications and Biologic Products**

No medications or biologic products will be administered as part of study procedures. As part of the standard of care at the site, subjects may receive anesthesia. Clinically necessary medications for the subjects' prescribed medical procedure shall be administered per the site standard care and participation in this study will not alter their standard care.

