##### **4.3.1 Enrollment Schedule**

After the first 5 subjects are enrolled and complete study procedures, subject enrollment will pause. A progress update will be submitted to the EC, which will include safety-related information such as any adverse events, device deficiencies, or any other relevant issues that have occurred during the initial enrollment period. Subject enrollment will resume upon receipt of favorable opinion from EC.

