## **5.2 Description of Study Procedures**

Eligible subjects will be enrolled into the study and positioned for their ultrasound exam. Standard clinical practice procedures will be followed using the standard of care device at the site to complete the clinically indicated exams.

After the clinically indicated exam, portions of the TTE and/or TEE exam will be repeated with the investigational Vivid E95 ultrasound device. Ultrasound scans in this study will take a similar amount of time and be performed in a similar manner as standard of care ultrasound exams at the site. The additional investigational TTE and TEE scans will add no more than about 15 minutes to the procedure time. For subjects having TEE in conjunction with surgery or an interventional catheterization procedure, the additional investigational scans will occur simultaneously while the hospital staff are preparing for or performing the procedure to avoid any delay in care. Images collected with the investigational device will not be used for patient management.

The device operator will store images from both ultrasound exams conducted with the standard of care device and the investigational device.

After completion of the investigational ultrasound exam, the ultrasound system and associated probes will be cleaned and disinfected as applicable, according to site standard of care and specifications in Sponsor instructions provided to the site.

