### **5.3 Follow-up**

Study enrollment will end after the subject has completed his/her investigational ultrasound exam. AEs reported to the site will be followed until resolution. No other follow-up procedures will be conducted.

Any data, including de-identified images, collected for the subject, up until the time of withdrawal or discontinuation, may still be provided to GEHC, unless the subject requests that their data not be used. The site shall document all requests by subjects regarding their data use.

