## **8.4 Reporting of Safety Events**

The following events are to be reported to the Sponsor within 72 hours of the event occurrence and to the EC per their policy:

- All SAEs and USADEs
- All device issues that could possibly lead to an SAE
- Any signal from an AE that might indicate a serious health threat
- Unanticipated AE and unanticipated ADEs

Additional follow-up information may be requested by the Sponsor. In addition, safety information may be shared with regulatory agencies and other participating sites, as required by applicable law and regulation.

The Sponsor contact for reporting safety events:

Research Program Integrator (see Appendix B)

E-mail: [REDACTED]

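### Adverse-event collection stops when the subject leaves the scan room, which is too early for subjects given a second, study-only TEE, possibly under anesthesia

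*Protocol*

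**What the plan says.** Sections 5.2 and 8.3 agree on the window. In the words of 8.3, "AEs will be collected from the time the ultrasound exam begins with the investigational device to the time the subject leaves the scan room". Section 5.2 adds that subjects may contact the investigator about later symptoms. Section 5.3 closes the matter: "AEs reported to the site will be followed until resolution. No other follow-up procedures will be conducted".

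Other sections describe who is exposed. Section 2.3.1 notes: "As part of the standard of care at the site, subjects may receive anesthesia". For subjects whose TEE accompanies surgery or catheterization, section 5.2 says that "the additional investigational scans will occur simultaneously while the hospital staff are preparing for or performing the procedure". Section 8.1.2 acknowledges that the second intubation may raise the overall chance of events, and section 2.5.1 classes the TEE probe as a significant risk device.

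Certain events must be "reported to the Sponsor within 72 hours of the event occurrence" (section 8.4). The list covers SAEs and USADEs, device issues that could lead to an SAE, signals of a serious health threat, and "Unanticipated AE and unanticipated ADEs".

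Three places use the result. The safety objective (3.1.2) is what kinds of AEs and SAEs occur and how many, section 10.3.2 reports the number, and the update sent to the ethics committee after the first 5 subjects covers "any adverse events, device deficiencies, or any other relevant issues that have occurred during the initial enrollment period" (4.3.1).

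**The concern.** The window suits a transthoracic scan of an awake subject. It suits an investigational TEE less well. That subject may leave the room still sedated or anesthetized, and some of the harms listed in 8.1.2 either need the subject to speak or take time to appear. With no later enquiry, a low count of throat symptoms or infections would partly reflect when the study stopped looking.

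At stake is the study's only safety output. There is no efficacy endpoint and no hypothesis, so the AE and SAE counts are the record of what the extra probe passage did to subjects, including children from 5 kg. The ethics committee also decides on resuming enrollment from an update drawn from the same collection process.

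**Working it through.** The protocol gives no figure to reproduce: the window is a rule, and the maximum of 100 subjects rests on sponsor experience. The check is to take the TEE hazards in 8.1.2 one at a time and ask whether the stated procedures would pick each one up.

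| Event (8.1.2) | Stated likelihood | Detectable before scan-room exit? | Route after exit |
|---|---|---|---|
| Throat irritation or discomfort | Uncommon | Only if the subject is awake and able to say so | Volunteered report; outside 8.4 if non-serious, because it is anticipated |
| Infection | Rare | Not expected; it would show later | Volunteered report; 8.4 if it meets the SAE definition and becomes known |
| Dental damage | Uncommon | Operator can see it | Volunteered report if noticed later |
| Bleeding | Rare | Operator can see it when visible | Volunteered report; 8.4 if serious and known |
| Perforation, including injury from pressure ischemia | Rare | Sometimes | 8.4 if serious and known |

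**Step 1: is any route after exit active?** No. Contact with the investigator (5.2) is at the subject's initiative. Section 5.3 follows AEs that have already been reported and rules out other follow-up procedures. Section 8.4 is a reporting duty, so it begins once someone knows of the event. None of the three asks the subject or a parent anything.

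**Step 2: which events have the weakest cover?** Section 8.4 reaches serious events, unanticipated events, device issues and health-threat signals. Throat irritation is listed in 8.1.2, so a non-serious case is neither serious nor unanticipated and 8.4 does not reach it. A mild, late infection is in the same position.

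**Step 3: do late reports count?** Section 8.3 begins by requiring every AE and SAE to be collected, then limits collection to the scan-room period. Section 5.3 follows reported AEs without an onset limit, 8.4 has no window, and 10.3.2 reports a number without saying which onsets qualify. Suppose a subject telephones the next morning with a sore throat. On the opening sentence of 8.3 the event adds 1 to the total; on the window sentence it adds 0. Both readings are reasonable.

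**Step 4: does this reach the restart decision?** The 4.3.1 update covers events in the initial enrollment period, so a late report already received belongs in it. Nothing prompts the first 5 subjects to make one.

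**The case against.** The strongest reply is that this is a deliberate and consistent design. Sections 5.2 and 8.3 give the same window, 2.5 says post-trial follow-up is not required, and participation is planned to last under a day. The study is an engineering pilot with no hypothesis or comparative claim, and 10.3.2 is a bare count. Several features limit the harm: exclusions 2, 4 and 5 remove higher-risk subjects, "The additional investigational TTE and TEE scans will add no more than about 15 minutes to the procedure time", and enrollment pauses after 5 subjects. In perioperative cases the room may be the procedure room, so the window may outlast the scan. Events found later would also be hard to attribute, because every investigational TEE follows a clinical one and there is no control group.

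Much of this stands. The design is consistent, the mitigations are real, and the attribution problem is a good reason not to insist on a next-day contact. The counting question alone would need only one clarifying sentence. The reply does not explain why collection should stop before an anesthetized subject can speak, since a check at recovery on the same day fits the planned duration. Exclusion 5 screens on the standard-device TEE and detects nothing caused by the second passage.

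A reader might infer that serious late injuries such as perforation escape the study altogether. The protocol does not support that: 8.4 has no scan-room limit, and such events are reportable once known.

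**Conclusion.** The concern holds for investigational-TEE subjects and should be corrected, although it does not invalidate the study. Followed as written, the window can undercount non-serious anticipated events and later-appearing events. This affects the AE totals for 3.1.2 and 10.3.2 and the update in 4.3.1. Serious and unanticipated events keep a route through 8.4, but that route depends on someone reporting them. TTE-only subjects, and events the operator sees in the room, are not affected.

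The size cannot be estimated. A reader might try to derive it from the share of TEE subjects who leave before waking. The protocol does not give that share, so the proportion of self-reported symptoms missed could lie anywhere from 0% to 100%. Such a calculation would also assume that awake subjects report fully, which very young children cannot do, and it would say nothing about infection.

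The conclusion assumes that some investigational-TEE subjects leave the room before they can report symptoms, or that some events appear only afterwards. If neither happens, the counts are unaffected and only the counting rule needs clarifying.

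**What to change.** - In 5.2 and 8.3, for subjects who have the investigational TEE, extend active AE collection to recovery from sedation or anesthesia, or to discharge from the recovery area if that is the same day. Include one brief check of throat pain, swallowing, bleeding and dental damage, asking the parent where the child cannot answer.
- In 8.3, state that AEs reported later through 5.2, 5.3 or 8.4 are documented with their onset and counted in the 10.3.2 totals and in the 4.3.1 update.
- Align 5.3, which now ends participation at the investigational exam and rules out other follow-up.
- Keep the present window for TTE-only subjects. A next-day contact is optional: it would lengthen participation and mostly find events that are hard to attribute.

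The cost is one CRF entry per TEE subject, with planned participation still under a day. The downside is that more events from the clinical TEE, anesthesia or surgery will be recorded and must be sorted with the device and procedure causality items already in 8.3. The counting sentence costs almost nothing and is worth adding even if the recovery check is declined.
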